For the outcome of SBT passage, if any of the above criteria are met during the 2 hour SBT, the patient will be labeled as failing the SBT for study purposes. Once any of these failure criteria are met, the respiratory therapist will alert the clinical team. The clinical team may choose to stop the SBT, in which case the patient will be returned to the previous ventilator settings, and weaning phase randomization will occur. If the patient is randomized to REDvent-weaning, they will be placed in PS/CPAP mode and pressure support will be titrated to achieve PRP between 200-400 (to max of 20). PEEP may be adjusted between 5 and 10 cmH₂O. The clinical team may alternatively choose to continue the SBT or to extubate the patient. If the patient is extubated, post-extubation management (and subsequent re-intubation management) will be usual care. If the patient is not extubated but the SBT is terminated by the clinical team, then weaning phase randomization will occur at that point.

Monitoring during the SBT will include placement of Respiratory Inductance Plethysmography (RIP) bands and a spirometer. Vital signs, physiologic measurements, and data from RIP and esophageal manometry will be recorded every 30 minutes during the SBT. A study ultrasound to measure diaphragm contractile activity will occur approximately 15 minutes into the SBT.

If the patient successfully passes the SBT, extubation readiness criteria will be confirmed (i.e. cough, gag, handling secretions, no procedures planned). If the patient meets extubation readiness criteria, the recommendation will be for extubation to the clinical team. If the patient does not meet extubation readiness criteria, they return to acute phase management (to whichever group they were randomized), and another SBT will be repeated 24 hours later. If a recommendation for extubation was given but actual extubation is delayed beyond 6 hours, the reasons will be recorded on the case report forms, and the acute phase intervention will be resumed. If the patient is extubated as recommended, the esophageal catheter and RIP bands will remain in place for 1 hour after extubation to monitor post-extubation effort of breathing.

If the patient fails the SBT, they will go on to the weaning phase randomization.

D.3.6 Weaning Phase: The weaning phase is defined as the time from the first SBT until the patient successfully passes an SBT.

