Comparison (a) REDvent-acute versus control: A 1-day reduction in length of weaning is considered clinically significant (less sedative exposure, fewer nosocomial infections, lower healthcare costs). With a sample size of 276 patients (138 per arm), up to 12% mortality and 1% attrition or incorrect randomization, a minimum of 240 patients (120 per arm) will be available for analysis of the acute phase. Power is based on 2 planned methods for analysis: cox proportional hazard ratios for multivariable analysis and univariate analysis with an independent t-test using log transformation (as needed) to account for the expected distribution of weaning duration. For univariate analysis using the assumptions above, we would be able to detect a ≥ 1 -day reduction in weaning duration with an alpha of 0.05 and power of 0.9 (Figure 7). For the cox proportional hazard model, we would be able to detect a relative hazard ratio of 1.5 (ratio between control/intervention group) with a power of 0.9 or a hazard ratio of 1.4 with a power of 0.8.

Comparison (b) REDvent-weaning versus control: Patients who fail the initial SBT will undergo the weaning phase randomization. From our pilot data, approximately 25% of patients exposed to the intervention passed the initial SBT, corroborating previous studies.¹⁵ Thus, at least 180 patients (90 per arm) will receive weaning phase interventions. Using the same assumptions as above, we will be able to detect a ≥ 1 day

reduction in the length of the weaning phase (Figure 8), or a hazard ratio of 1.5 with an alpha of 0.05 and power of 0.8. Patients who do not pass the SBT by 28 days post the weaning phase randomization will be censored for analysis, as study interventions and daily monitoring will end on day 29.

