The primary analysis seeks to address if there are differences in length of weaning between: 1) REDvent-acute compared to usual care acute, 2) REDvent-weaning compared to usual care-weaning, and 3) REDvent-acute and weaning (combined) compared to usual care acute and weaning (combined). Analyses of these aims will follow the ITT principle. The primary analyses will compare median weaning duration between groups using a Mann-Whitney U test, or a t-test with transformation as necessary. The effect size (r) will also be computed to assess the magnitude of treatment effect. If imbalances in baseline characteristics are found between or across randomized treatment groups, a Cox proportional hazard model will be performed to adjust for covariates. The estimates (mean, median, or hazard ratio) and the associated 95% confidence interval, as well as the p-values, will be presented for interpretation.

Power analysis: For the primary outcome (weaning duration), a 1-day change in length of weaning is considered clinically significant. It is anticipated that up to 20% of patients may not achieve the primary outcome (successful passage of an SBT or extubation due to death or dropout); these patients will not be included in the primary outcome analysis but will be included in secondary outcomes. We are targeting an overall sample size of 300 patients, with a minimum of 240 patients (120 per arm) available for analysis of the primary outcome. Using the planned statistical tests above, this sample size would be able to detect a ≥ 1 -day change in weaning duration with a two-sided alpha of 0.05 and power of 0.9, or a relative hazard ratio of 1.5 (ratio between control/intervention group) with a power of 0.9 or a hazard ratio of 1.4 with a power of 0.8. Patients who fail the initial SBT will undergo the weaning phase randomization. From our pilot data, approximately 25% of patients exposed to the intervention passed the initial SBT. Anticipating 180 patients (90 per arm) will receive weaning phase interventions, there will be adequate power to detect a ≥ 1 day change in the length of the weaning phase, or a hazard ratio of 1.5 with an alpha of 0.05 and power of 0.8 in the weaning phase.

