After the first 75 patients were enrolled in the study a new milestone accrual plan was created to account for the increase in the percentage of patients meeting the primary outcome. Previously, it was assumed 20% of patients would not meet the outcome, however, data after 75 patients revealed this was 13% and the total sample size requirement was adjusted down from 300 to 276 patients. The number of patients targeted per group to meet the primary outcome was unchanged, at 120 per group. This updated milestone accrual plan was reviewed and accepted by the NLHBI and DSMB.

January 2023 - Change in primary analysis for length of weaning

Blinded, non-inferential summary statistics and distributions were assessed for the length of weaning outcome by the primary statistician as part of the data cleaning process. It was revealed that length of weaning might not be optimally analyzed as a continuous variable because SBTs were conducted once a day, with most patients passing their SBT within the first three days. In addition, enrollment had been affected by the COVID-19 pandemic and a new milestone accrual plan was requested by the NHLBI. As the observed distribution appeared more count-like, the primary analysis model was changed to Poisson or Negative binomial regression to better fit the data and satisfy assumptions. This decision was made by the senior biostatistician who was blinded to the randomization groups.

The sample size was re-estimated based on a minimum detectable difference for a reduction in the number of weaning days in the REDvent-acute vs. usual care-acute group using negative binomial regression. This yielded a minimal sample size of 230 patients to detect a reduction of 0.36 to 0.75 days when usual care had an average number of weaning days between 1 and 4, respectively with a power of 80%. This estimate of 230 patients accounted for the 13% loss in those meeting the primary outcome. This updated sample size estimate was reviewed and accepted by the NHLBI and DSMB. Based on this, the milestone accrual plan was revised, and enrollment was planned to continue through March 2024 with a target sample size between 230-276.

May 2024 – Change in primary analysis for length of weaning and PiMax

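### When the minimum enrolment fell to 230, only the acute comparison was re-powered; the final SAP still claims power 0.8 with 180 children for REDvent-weaning, against about 0.69 to 0.70 with 150 at that minimum

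*Combined protocol and SAP*

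**What the plan says.** The final SAP (July 2024) names three primary comparisons of weaning duration: REDvent-acute against usual care, REDvent-weaning against usual care, and both phases combined.

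Its Power analysis paragraph is the one in the Fall 2019 SAP. It allows up to 20% loss and says: "We are targeting an overall sample size of 300 patients, with a minimum of 240 patients (120 per arm) available for analysis". For the acute comparison it claims a one-day change "with a two-sided alpha of 0.05 and power of 0.9, or a relative hazard ratio of 1.5". For the weaning comparison it says "Anticipating 180 patients (90 per arm) will receive weaning phase interventions" and claims adequate power for one day, "or a hazard ratio of 1.5 with an alpha of 0.05 and power of 0.8 in the weaning phase".

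Two dated entries later in the same SAP change the sizes:

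- October 2019: loss revised to 13% and enrolment to 276, with 120 per group unchanged.
- January 2023: a re-estimate for REDvent-acute against usual care, by negative binomial regression at 80% power. "This yielded a minimal sample size of 230 patients", and "This estimate of 230 patients accounted for the 13% loss in those meeting the primary outcome". The enrolment target becomes 230 to 276, accepted by the funder and the DSMB.

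No entry gives a power for the weaning comparison at the new minimum.

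The current protocol, D.6.4.1, Comparison (b), starts from 276 enrolled and at least 240 evaluable, and says: "Thus, at least 180 patients (90 per arm) will receive weaning phase" interventions. Section D.3.5 lets the clinical team extubate a child who has met a failure criterion: "If the patient is extubated, post-extubation management (and subsequent re-intubation management) will be usual care". It provides for weaning randomisation when the child is not extubated and the team ends the trial of spontaneous breathing.

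**The concern.** The power paragraph is written as current and nothing marks it as superseded, although other parts of the final SAP body were updated (the upper age limit and the enrolment window, for example). A reader who wants the power of the weaning comparison finds only 0.8 with 180 children. The enrolment range in force does not guarantee 180. A null result for REDvent-weaning could be set against a power that the plan does not deliver at its permitted minimum.

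**Working it through.** Inputs:

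- Effect: one day, or hazard ratio 1.5; two-sided alpha 0.05; 1:1 allocation (final SAP).
- SD: 2.1 days (pilot intervention) and 2.8 days (historical controls), from protocol D.6.4.1. Root mean square: √((2.1² + 2.8²)/2) = 2.475.
- Loss: 13% (January 2023 entry).
- First-SBT pass rate: 25%, so 75% go on to weaning randomisation, applied to all children as the plan does.
- For the Cox figure, every child counts as an event, which is favourable to the plan.

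**Step 1. Numbers of children.**

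- 276 × 0.87 = 240 evaluable; 240 × 0.75 = 180 weaning-randomised (90 per arm).
- 230 × 0.87 = 200 evaluable; 200 × 0.75 = 150 weaning-randomised (75 per arm).

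The reading that 230 enrolled means 100 evaluable per arm can be checked against the January 2023 figures. With no over-dispersion, power is Φ(|ln(m₂/m₁)| / √((1/m₁ + 1/m₂)/100) − 1.96). A fall from 1 to 0.64 days gives 0.796 and a fall from 4 to 3.25 days gives 0.794. Both match the stated 80%.

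**Step 2. The plan's own figures.** For one day, power ≈ Φ(1/(SD × √(2/n)) − 1.96) with n per arm; the exact t-test figure is slightly lower. For the hazard ratio, power = Φ(½√d × ln 1.5 − 1.96) with d events.

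- 120 per arm: one day 0.876 (t-test); hazard ratio 1.5 with 240 events, 0.881. Stated: 0.9.
- 90 per arm: one day, Φ(1/0.369 − 1.96) = 0.774, t-test 0.769; hazard ratio 1.5, Φ(6.708 × 0.4055 − 1.96) = 0.776. Stated: 0.8.

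With the simple average SD of 2.45, the one-day normal figures are 0.885 and 0.782. The stated powers are therefore reproduced to within 2 to 3 points.

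**Step 3. The weaning comparison across the range in force.**

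| Enrolled | Evaluable | Weaning-randomised | Power, 1 day (t-test) | Power, HR 1.5 |
|---|---|---|---|---|
| 276 | 240 | 180 | 0.769 | 0.776 |
| 230 | 200 | 150 | 0.691 | 0.70 |

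At 75 per arm the normal formula gives Φ(1/0.404 − 1.96) = 0.697 for one day. With SD 2.45 the t-test figure is 0.700, so the choice of SD summary hardly matters.

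**Step 4. Effect detectable with 150 children at power 0.8.**

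- Difference: 2.80 × 2.475 × √(2/75) = 1.13 days by the normal formula, 1.14 by the t-test.
- Hazard ratio: exp(2 × 2.80/√150) = 1.58.

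**The case against.** The strongest reply is that the final SAP is built as retained text plus dated changes, and that the January 2023 entry openly resets the sample size. For the acute comparison this is right. A reader might infer that the SAP hides a fall from 0.9 to about 0.81 there. The documents do not support that: the entry itself states 80% power at 230 enrolled, for a different effect and model, accepted by the funder and the DSMB. For that comparison the power paragraph is only unmarked old text.

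Second, 230 is a floor. At 276 enrolled the 240 and 180 return. Final enrolment is not given, so nobody can say from these documents that the weaning comparison had power 0.69. Nor is the whole gap between 0.8 and 0.69 due to the lower enrolment: on one formula the fall is from 0.77 to 0.69, about 8 points, and the rest was there at 180.

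Third, a reader might infer that 180 is a ceiling, because it is 75% of 240 and children extubated after a failed first SBT are not weaning-randomised. That is not established. The protocol calls 240 a minimum. The 25% pass rate comes from pilot patients who received the intervention, so a lower pass rate in controls would send more children to weaning randomisation. No rate is given for extubation after a failed SBT.

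Fourth, the t-test and Cox models were later set aside. The SAP moved to negative binomial regression, then based its conclusions on proportional odds and reported that proportional hazards did not hold. So the figures above are not the power of the final model. That power cannot be derived, because no dispersion is stated. With 75 per arm and a fall from 4 to 3 days, the negative binomial formula gives 0.90 with no over-dispersion, but 0.68 to 0.53 if dispersion is assumed at 0.24 to 0.46, values inferred from the pilot means and SDs. This is a reason to label the figures; it does not rescue the stated 0.8.

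Last, data collection was complete by May 2024, and the SAP requires estimates with 95% confidence intervals, which limits over-reading of a null result. That lowers the stakes but leaves the text wrong.

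**Conclusion.** The point stands for the weaning comparison. It is a named primary comparison, it was not re-powered when the minimum enrolment fell to 230, and the stated 0.8 with 180 children is not delivered at that minimum. There, about 150 children would be weaning-randomised, with power about 0.69 for one day and 0.70 for a hazard ratio of 1.5. At 276 enrolled the figures are 0.77 and 0.78, close to what is stated.

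This rests on the pilot SDs of 2.1 and 2.8, two-sided 0.05, 13% loss, 75% first-SBT failure in all children, every child an event for the Cox figure, and the original t-test and Cox models. It does not show an undisclosed loss of power in the acute comparison, a cap of 180 on weaning randomisation, or the power actually achieved.

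**What to change.** In the final SAP, mark the power paragraph as superseded and state the sizes in force: 230 to 276 enrolled, about 200 to 240 evaluable, and about 150 to 180 weaning-randomised.

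- Acute comparison: refer to the 80% re-estimate in the January 2023 entry.
- Weaning comparison: state power of about 0.69 to 0.77 for one day and 0.70 to 0.78 for a hazard ratio of 1.5, and the effect detectable with 150 children at power 0.8 (1.14 days or hazard ratio 1.58). Label these as computed under the original t-test and Cox assumptions, not the later negative binomial or proportional odds model.
- Protocol D.6.4.1, Comparison (b): replace the lower bound of 180 with about 150 to 180, and note that children extubated after a failed first SBT are not weaning-randomised.

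The cost is wording in two documents. No enrolment, analysis or decision rule changes; the stated power for the weaning comparison becomes less favourable.

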We will measure patient effort of breathing twice daily with esophageal manometry (using Pressure Rate Product [PRP] and Pressure Time Product [PTP]) and once daily using diaphragm ultrasound (using Diaphragm Contractile Activity [DCA]), during the acute and weaning phases in both arms. DCA is obtained by measuring the thickness of the right hemi-diaphragm and calculating the percent difference between diaphragm thickness on inspiration and exhalation. Diaphragm ultrasound measurements will be performed independently by 2 practitioners, one of whom is specifically trained in acute care ultrasound. We will also use ultrasound to measure diaphragm thickness on exhalation and monitor how this changes serially over time as a measure of the architecture of the diaphragm. Finally, we will measure respiratory load (resistance, compliance) daily using spirometry. The clinical team will remain blinded to the results of these measurements in both arms.

D.4.2. Spontaneous Breathing trial respiratory measurements during Airway Occlusion:

Airway Occlusion: Prior to each SBT, we will perform a standardized airway occlusion maneuver to measure neuromuscular capacity with aPiMax (airway) and ePiMax (esophageal), as described in the Preliminary Data. In addition, during airway occlusion we will measure DCA (as above)^{5, 7, 51, 52}, to provide complementary data to PiMax. The clinical team will remain blinded to the results of these measurements in both arms.

D.4.3 Weaning trial measurements during SBTs:

During SBTs, respiratory effort and capacity will be measured with PRP, PTP, inspiratory pressure from esophageal manometry (Pi), Pi/ePiMax, Tension Time Index (TTI), Phase angle (PA), and DCA. Patients will be monitored continuously during the SBT, and all of these measures will be recorded at the beginning of the SBT, and then every 30 minutes (for 5 minute periods) to monitor respiratory muscle endurance over time. The PRP measurements will be shared with the clinical team in both arms because they will be used to help define passage of SBTs (as above). Clinical providers will remain blinded to the results of the other measurements in both arms.

Data Collection timeline	Enrollment	Acute (Daily)	Weaning (Daily)	SBT	Post-Extubation
Demographics (age, race, gender, past medical history, primary diagnoses, comorbidities, PRISM-III-12 severity of illness scores, height, weight, quality of life score)					

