D.6.2 Rationale for Randomization Strategy: Age stratified randomization is necessary because *age is an important biological variable* likely to confound the relationship between respiratory muscle weakness and length of weaning. This will ensure an equal age distribution amongst treatment groups. Age groups are based upon accepted pediatric definitions, and have been used in numerous other pediatric RCTs. Neonates (< 1 month) have been excluded because they are often managed with different ventilator strategies and because normal values for PiMax are lower in neonates ^{63, 64}. Immunosuppression is a known risk factor which affects duration of ventilation and weaning, and an imbalance in immunosuppression between groups has been shown to significantly confound previous pediatric mechanical ventilation studies. The additional weaning phase randomization is necessary because we anticipate an imbalance of the number of patients who will be extubated after the acute phase between REDvent-acute and control groups. Acute phase management may have a sustained effect on neuromuscular strength that will affect the duration of weaning. To understand whether the REDvent strategy during the weaning phase can prevent prolonged weaning, risk factors for prolonged weaning (which may be different based on acute phase management) need to be rebalanced with a second randomization. Ultimately, this will allow us to determine the independent utility of REDvent-acute and REDvent-weaning components.

D.6.3 Preparation of the Analysis Data Set

Datasets for analyses consist only of data for which all queries have been resolved. In addition to data management steps to reduce error in data acquisition and entry, a biostatistical cleaning will focus on inconsistencies, missing data and outliers in variables related to the derivation of key outcomes. These activities will be ongoing throughout the study and will involve both the data management team and the biostatistics team.

Preplanned construction of new variables will be conducted in accordance with the study hypotheses and analysis plans. Variable transformation may be required for interpretive

and statistical purposes. With respect to the primary outcome of weaning duration, patients who do not progress to the weaning phase within 28 days (i.e. death, prolonged severe illness) will not be included in analysis of the primary outcome, but will be considered for secondary outcomes.

D.6.4 Statistical Analysis Plan

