Comparison (c) REDvent versus control both phases: We will get an assessment of the cumulative effect of the intervention by comparing patients who received both REDvent-acute and REDvent weaning to patients who received only usual care in both phases. Because the rates of passage of the first SBT will differ between groups, there will not be an equal number of patients exposed to REDvent only as control only. Based on the assumptions above, we anticipate that of the 240 patients included in the analysis of weaning duration, 78 will be REDvent only, 72 will be control only, and 90 will be mixed. As such, the expected sample size comparing REDvent only to control only would allow us to detect a ≥ 1.1 - day reduction in weaning duration with a hazard ratio of 1.6 with a power of 0.8 and alpha of 0.05; or a ≥ 1.3 - day reduction in weaning duration with a hazard ratio of 1.6 with a power of 0.9.

All patients will be analyzed in the groups to which they were randomized for weaning duration, following intention to treat principles (allow for up to 1% incorrect allocation or attrition). Clinical variables (data collection table) will be tracked and compared between intervention and control groups for all 3 of the planned analyses (a-c). If there is an imbalance in any variable that may confound the relationship between weaning duration and REDvent, we will build a multivariable cox proportional hazard model to ensure that the measured treatment effect on weaning duration is retained after multivariable adjustment.

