Additional details are also available in the published study protocol.² Baseline characteristics at the time of randomization will be computed for each treatment group (REDvent and usual care) and within each phase (Acute and Weaning). For all analyses, assumptions for data distribution will be assessed, and normalizing transformations of the data or nonparametric analysis will be performed as necessary. The mean and standard deviation will be reported for normally distributed continuous variables, and the median and interquartile ranges will be reported for non-normally distributed continuous variables. Given this is an RCT, we anticipate balanced baseline characteristics. To evaluate this, we will calculate effect sizes for measures of central tendency (Cohen d, Cramer v) across groups. For non-parametric

variables, effect sizes defined for the Mann-Whitney U will be calculated to produce r . For frequency counts and percentages the rate ratio will be evaluated to calculate the effect size. Variables that have more than a small effect size ($d > 0.2$, $v > 0.01$, or $r > 0.1$, categorical effect size >1.2) indicate potential imbalances in baseline characteristics between groups. These variables will be included in sensitivity analyses after the primary ITT analyses are performed or included as covariates using multivariable models.

Retention, adherence, and missing data will be compared across groups. High levels of missing data are not anticipated given the nature of the study. If the missing data are determined to be related to the outcome (not missing at random) or related to group or a covariate (missing at random), we will explore the impact of these biases in sensitivity analyses after the primary ITT analyses using multiple imputation processes. Our primary approach to imputing missing data is the Markov Chain Monte Carlo (MCMC) simulation. Statistical Analysis Software (SAS) procedures will be used.

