The analytic approach for secondary aims and outcomes such as mortality and ventilator free days will follow those described above. For categorical data, a χ^2 or Fisher's exact test will be used to compare difference between groups. Logistic regression will be used to assess binary outcomes, and a multinomial/ordinal logistic regression will be used for categorical outcomes (> 2 categories) while adjusting for covariates. To assess the association between 2 continuous variables, a Pearson or Spearman correlation will be used, and analysis of covariance (ANCOVA) will be used to adjust for covariates. Generalized Estimating Equations (GEE) or mixed effect models will be used when necessary to analyze repeated measures. Because of the physiologic nature of the study with a Phase II design,

multiple comparisons adjustment is not planned for secondary outcomes. Analyses will be performed using the appropriate recent version of the SAS statistical software (SAS Institute Inc., Cary, NC).

In order to increase precision around the effect estimates for the primary and secondary aims and to reflect the stratified sampling, all analyses are adjusted for block randomization variables.³ For acute phase these are age group (infant, child, and adolescent) and whether or not the subject was immunocompromised. For the weaning phase this is acute phase randomization grouping and age group. In addition, variables thought to be potential confounders on the relationship between intervention and outcome with large differences between groups (standardized effect sizes as detailed above) will also be included in all adjusted analyses. Unadjusted analyses will be presented to summarize data; all primary and secondary outcomes will present adjusted analyses controlling for age category, immunosuppression and imbalanced baseline variables. Potential confounders will be assessed for multicollinearity and if present, the confounder with the highest biological plausibility to impact the effect of the intervention on the outcome will be selected for inclusion as a model covariate.

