Because the pre-specified plan was to use a negative binomial model, those findings have been presented in the main results, but because the model does not appropriately fit the data due to the highly influential outliers, the conclusions and abstract results reflect the more appropriate proportional odds model. This model was agreed upon by the study statistical team and DSMB statisticians in June 2024 at the final DSMB meeting.

PiMax was planned to be modeled with linear regression, with truncation of values >100. In the analysis, no transformation could satisfy the assumptions of linear regression, with poor model diagnostics and non-normality of residuals. PiMax was therefore modeled with the proportional odds model given the non-parametric nature of the data. No specific categories were created for PiMax, but instead it was treated as a rank-based variable with comparisons of ranks between groups, adjusting for blocking variables and confounders (oxygenation index). The model allowed us to compare the odds of a higher PiMax ranking for the REDvent vs. usual care groups. Table 1 has been revised and now presents the description of all outcome variables, initial planned analyses, and modifications to initial proposed analyses and the timing of those changes. In addition, since all outcomes are presented as adjusted analyses, Table 2 details the four main modeling approaches used in these analyses, and interpretation of the model intervention parameter estimates.

References

1. [name] RG, Smith LS, Zimmerman JJ, et al. Pediatric Acute Respiratory Distress Syndrome: Definition, Incidence, and Epidemiology: Proceedings From the Pediatric Acute Lung Injury Consensus Conference. *Pediatric Critical Care Medicine*. Jun 01 2015;16(5_suppl):S23-S40. doi:10.1097/PCC.0000000000000432
2. [name] RG, Hotz JC, Klein MJ, et al. A Phase II randomized controlled trial for lung and diaphragm protective ventilation (Real-time Effort Driven VENTilator management). *Contemp Clin Trials*. Jan 2020;88:105893. doi:10.1016/j.cct.2019.105893
4. Firth D. Bias Reduction of Maximum Likelihood Estimates. *Biometrika* 1993. p. 27-38.

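### Beyond the blocking variables, covariates are chosen by chance imbalance between arms and not by prognostic value, so some precision is forgone

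*Combined protocol and SAP*

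**What the plan says.** - **Blocking variables.** The final SAP states that "all analyses are adjusted for block randomization variables", with greater precision as a stated aim. For the acute phase these are age group and immune status. For the weaning phase they are acute-phase arm and age group.
- **Everything else.** The same paragraph adds only "variables thought to be potential confounders on the relationship between intervention and outcome with large differences between groups", and describes the reported models as "controlling for age category, immunosuppression and imbalanced baseline variables".
- **The screen.** Two paragraphs earlier the trigger is worded differently: "Variables that have more than a small effect size" are flagged. The thresholds are d above 0.2, Cramér V above 0.01, r above 0.1 and a categorical effect size above 1.2. Flagged variables may go either to sensitivity analyses or into multivariable models.
- **Primary analysis.** The SAP's primary-analysis paragraph calls for a covariate-adjusted Cox model only where imbalance is found. Protocol D.6.4.1 has the same trigger: "If there is an imbalance in any variable that may confound the relationship between weaning duration and REDvent", a multivariable Cox model follows.
- **What is available.** The data collection timeline in D4 lists "PRISM-III-12 severity of illness scores" and hypoxaemia markers. No non-blocking covariate is named in advance for length of weaning. The note on PiMax reports "adjusting for blocking variables and confounders (oxygenation index") but does not say whether prognosis or imbalance brought that variable in.

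**The concern.** After randomisation, any baseline difference between arms is chance, and the SAP itself expects balance. What a covariate contributes to the treatment estimate depends on how well it predicts the outcome. A strong predictor that happens to be balanced stays out, and its variance remains in the error term. A weak one that happens to differ goes in. The set can change from one comparison to the next and cannot be known until data by arm are examined.

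The rule is also not fully determined. More than a small effect is not the same threshold as a large difference, and one paragraph leaves open whether flagged variables enter the main model while another puts them into all adjusted analyses.

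At stake is precision on the primary outcome, in a trial whose minimum enrolment was lowered to 230, and how far a reader can reconstruct the adjusted results.

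**Working it through.** **Inputs from the documents.** SDs of 2.1 and 2.8 days and a 1-day difference (D.6.4.1); two-sided alpha 0.05 (SAP power analysis); minimum enrolment 230 with 13% loss (SAP, January 2023 note); 25% passing the first SBT (SAP power analysis).

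**Assumption.** R², the share of outcome variation explained by the added covariates beyond the blocking variables. The documents give none, so 0.05 to 0.30 is shown.

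**Step 1. The plan's own power.** For January 2023, power = Φ(|ln(m1/m0)| / √((1/m0 + 1/m1)/n) − 1.96), with n = 100 per arm.
- Mean 1 against 0.64 days: 0.446/0.160 − 1.96 = 0.83, power 0.796.
- Mean 4 against 3.25 days: 0.208/0.0747 − 1.96 = 0.82, power 0.794.

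Both match the stated 80%, with no overdispersion and no credit for covariates. The earlier sizing (1 day, 120 per arm) gives 0.879 against a stated 0.9, again without covariates.

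**Step 2. Sample sizes.** 230 × 0.87 = 200, or 100 per arm. For weaning, 200 × 0.75 = 150, or 75 per arm.

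**Step 3. Effect.** Root-mean-square SD = √((2.1² + 2.8²)/2) = 2.475, so 1 day is 1/2.475 = 0.404 SD.

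**Step 4. Always adjusting, by formula.** Power = Φ(0.404 × √(n/2) / √(1 − R²) − 1.96). At n = 100 the unadjusted noncentrality is 0.404 × 7.07 = 2.857, power 0.815. Dividing by √(1 − R²) gives 0.834, 0.853, 0.891 and 0.927 for R² of 0.05, 0.1, 0.2 and 0.3.

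**Step 5. Against the SAP's rule.** The triggered rule already recovers part of that gain, so the fair comparison is simulated: 8,000 trials per cell, a linear model, and the covariate added only if |d| > 0.2. Ranges are across repeated runs.

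| Per arm | R² | Triggered | Always adjusted | Gap (points) |
|---|---|---|---|---|
| 100 | 0.05 | – | – | 1.7 |
| 100 | 0.1 | 0.815–0.825 | 0.846–0.849 | 2.4–3.1 |
| 100 | 0.2 | 0.835 | 0.889 | 5.4 |
| 100 | 0.3 | 0.848–0.850 | 0.926–0.928 | 7.8–7.9 |
| 75 | 0.05 | – | – | 1.5 |
| 75 | 0.2 | 0.718–0.719 | 0.782–0.787 | 6.4–6.8 |
| 75 | 0.3 | – | – | 9.6 |

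(A dash means only the gap was recorded.)

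**Step 6. Type I error.** For the triggered rule it lies between about 0.03 and 0.05, lower as R² rises. When the covariate is balanced and omitted, the unadjusted standard error is too large for the variation that remains, so the test is mildly conservative.

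**Step 7. How often chance trips the screen.** For d > 0.2: 2[1 − Φ(0.2/√(2/n))] = 0.157 at 100 per arm and 0.221 at 75. For V > 0.01 on a binary variable with 200 patients: 2[1 − Φ(0.01 × √200)] = 0.888. For binary variables the screen removes almost nothing, and selection falls to what is thought to be a confounder.

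**Step 8. A check closer to the reported model.** A six-category proportional-odds simulation (200 patients, 1,000 runs per setting, assumed category shares) gave gains of 1.8, 4.1, 6.0, 10.6 and 12.4 points at latent R² of 0.05, 0.10, 0.15, 0.20 and 0.25. These are against never adjusting for the covariate, so they overstate the gain over the triggered rule.

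**The case against.** The best defence is that the SAP already secures much of what adjustment offers. It adjusts for age and immune status in the acute models. Protocol D.6.2 picks out exactly these as prognostic: "Immunosuppression is a known risk factor which affects duration of ventilation and weaning". What PRISM-III-12 or oxygenation index would add for weaning duration is unknown and could be small. The clock starts at the first SBT, after the acute phase has resolved, and every patient has just passed an oxygenation test (C.3.1), which narrows the range of any oxygenation measure taken then. All of this stands, and it is why the low end of the R² range deserves as much weight as the high end.

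Four stronger readings are tempting, and the documents do not support them.
- A reader might infer that 5 to 10 points of power are lost. No R² is given, the gap is below 3 points or so at R² up to 0.1, and it nears 10 only at 75 per arm with R² of 0.3. No stated power figure credits covariate adjustment, so nothing falls short of plan.
- A reader might infer inflated type I error. The simulations show the reverse. The screen looks at baselines by arm, not at outcomes.
- A reader might infer that disease severity went unadjusted. Oxygenation index is named for PiMax. The May 2024 note says the alternative primary models carried the same confounders as the negative binomial model, but does not list them.
- A reader might take the table as the power of the actual analysis. It pairs the earlier 1-day effect with the later minimum enrolment in a linear model, while the SAP moved to negative binomial and then proportional-odds regression. The enrolment target was 230 to 276, so 230 is the lower bound. Only the d trigger is modelled.

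**Conclusion.** The point holds as a matter of method. Selecting non-blocking covariates by observed imbalance is inefficient, is settled only after data by arm are seen, and is worded inconsistently within the SAP. Under the linear proxy at 100 per arm, the forgone gain is about 2 to 3 points of power for R² of 0.05 to 0.1 and about 5 to 8 points for 0.2 to 0.3. Those R² values are assumed, so the size is a range and not a finding about this trial. Validity is not threatened. This is an improvement available at little cost, together with a gap in reporting: the confounders used for the primary outcome, and the route by which each entered, are not stated.

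**What to change.** Replace the trigger with one fixed list chosen for prognostic value and adjusted for whatever the observed balance.
- **Acute comparison:** blocking variables, baseline oxygenation index and PRISM-III-12. If OSI is preferred to oxygenation index, name it as the single measure. Eligibility accepts either index, so check availability before choosing.
- **Weaning comparison:** its blocking variables, days ventilated at the first SBT and one severity measure chosen in advance. Days ventilated precedes the weaning randomisation, so it is a proper baseline there. It is not one for the acute comparison.
- **Imbalance screen:** keep it only for a labelled sensitivity analysis.
- **Wording:** settle on one threshold (more than small, or large) and one role for flagged variables (sensitivity analysis, or covariate in all adjusted models).
- **Disclosure:** list the confounders actually used in the primary model and why each entered.

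The unblinded statistician was checking the primary model in May 2024, before this SAP was finalised. A list fixed now is itself a choice made after unblinding. Any re-run with it should be reported as post hoc alongside the existing result, not in its place. The cost is SAP wording, a re-run on variables already collected and a few degrees of freedom.
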